NCT# 03803475

Gallium-68 PSMA-11 PET in prostate cancer patients

[figure not shown]
Study Drug: Gallium-68 PSMA-11

Version: 1.3

Version Date: November 26, 2019

Principal Investigator (Sponsor-Investigator)

[name]
University of California San Francisco

Revision History

Version 1.0	10/06/2018
Version 1.1	03/04/2019
Version 1.2	04/02/2019

Protocol Signature Page

Protocol No.: 185513

Version Date: 26NOV2019

1. I agree to follow this protocol version as approved by the UCSF Protocol Review Committee (PRC), Committee on Human Research (CHR), and Data Safety Monitoring Committee (DSMC).
2. I will conduct the study in accordance with applicable CHR requirements, Federal regulations, and state and local laws to maintain the protection of the rights and welfare of study participants.
3. I certify that I, and the study staff, have received the requisite training to conduct this research protocol.
4. I have read and understand the information in the Investigators' Brochure (or Manufacturer's Brochure) regarding the risks and potential benefits. I agree to conduct the protocol in accordance with Good Clinical Practices (ICH-GCP), the applicable ethical principles, the Statement of Investigator (Form FDA 1572), and with local regulatory requirements. In accordance with the FDA Modernization Act, I will ensure the registration of the trial on the www.clinicaltrials.gov website.
5. I agree to maintain adequate and accurate records in accordance with CHR policies, Federal, state and local laws and regulations.

UCSF Principal Investigator / Study Chair

Printed Name

Signature

Date

Abstract

Title	Gallium-68 PSMA-11 PET in prostate cancer patients
Patient population	Patients with biopsy proven prostate cancer who have a concern for metastatic disease.
Rationale for Study	Gallium-68 PSMA-11 has been shown to have a higher sensitivity for the detection of metastatic prostate cancer than conventional imaging.
Primary Objective	Determine detection rate of PSMA-11 PET broken down by PSA
Study Design	This is a single center open label study.
Number of patients	Total population of patients will be 1,000 patients.
Duration of Therapy	The study will involve a single imaging study.
Duration of Follow up	No follow-up will be performed.
Duration of study	The study will reach completion two years from the time the study opens to accrual.
Study Drugs	Gallium-68 labeled PSMA-11 (PSMA-HBED-CC)
Safety Assessments	The patients will also be asked to report adverse events.

1.1 Overview

Imaging and staging of prostate cancer is critical for surgical and treatment planning. We aim to image patients with suspected metastatic prostate cancer using Gallium-68 labeled HBED-CC PSMA (more commonly called ^{68}Ga -PSMA-11) in order to demonstrate its utility. We plan to utilize this data to obtain further approvals of the ^{68}Ga -PSMA-11 compound, so that this agent will become available for clinical imaging in prostate cancer patients.

This compound has been shown to be superior to choline based PET agents for the staging of prostate cancer, both Carbon-11 and Fluorine-18 compounds. But this compound was not patented and therefore no company or private entity will make the investment required to bring PSMA-11 to market. In the vacuum of availability, academic groups must take the lead in order to collect the necessary data for future FDA approval. This protocol was developed in collaboration with the Clinical Trials Network of the Society of Nuclear Medicine and Molecular Imaging. The inclusion criteria and study endpoints have been aligned so that inter-institutional sharing of data can be performed in order to pool data for final NDA submission.

1.2 Background

Prostate cancer is the most commonly diagnosed cancer and second leading cause of cancer death in American men (1). Existing conventional imaging (CT, MRI and bone scans) has a low sensitivity in detecting local recurrence or metastatic disease (2). The one exception being NaF PET/CT for the detection of osseous metastasis. Due to this limitation, numerous approaches to stage patients have been evaluated.

Choline imaging has been frequently used, as prostate cancer exhibits increase choline uptake that has been associated with the presence of choline kinase (3). Choline uptake is increased in comparison to FDG in both androgen dependent and independent prostate cancer patients (4). Choline has also been shown to be sensitive for the detection of recurrent tumor in patients with PSA (prostate specific antigen) values of less than 1.0 ng/ml (5). There are two forms of choline that are used in imaging prostate cancer, C-11 and F-18 choline. C-11 choline has a short half-life of 20 minutes, which limits its detection for metastatic disease but results in improved local detection due to decreased urinary activity at the time of imaging. F-18 choline has significant urinary excretion that limits evaluation of the prostate but, but has been shown to have better detection rates for distant metastatic disease (6). C-11 choline has limited sensitivity for osseous metastasis, possibly due to the decreased uptake time (7). Additionally, the sensitivity of C-11 choline is limited in patients with PSA values < 1.0 ng/ml (8-10). Although choline PET may be limited in sensitivity, it clearly delineates more lesions than cross section imaging or bone scan in patients with known disease (11). In 2012, the Mayo Clinic obtained NDA (new drug application) approval from the FDA for the use of C-11 choline.

A separate approach is to image the prostate specific membrane antigen (PSMA). PSMA is expressed on the majority of prostate cancer cells, and so would be an ideal cell membrane protein to image. The initial imaging approach to PSMA imaging target the intracellular domain using Indium-111-capromab (Prostascint), a murine monoclonal antibody (12,13). Although there was early promise for the detection of nodal metastasis (14), the agent was never able to adequately visualize osseous metastasis (15). Although combination with SPECT/CT does

improve lesion detection (16). One main limitation to In-111-capromab is that it takes a prolonged time to localize to the target tissue, which likely relates to both the size of the monoclonal antibody and the fact that agent targets the intracellular domain of the PSMA protein. Additionally, Proscint also recognizes an intracellular epitope so the antibody must cross the membrane to be effective. This likely only occurs in permeable dead or dying tumor cells.

Because of the limitations of In-111 capromab, there has been continued effort to develop agents that target the extracellular domain of the PSMA protein. The Ga-68 labeled PSMA-11 compound has become of particular interest because in the last year there have been two important articles. The first demonstrates that PSMA-11 has a higher sensitivity for the detection of disease than F-18 choline in a head-to-head intra-patient comparison that included 37 patients (17). The second paper looked at the sensitivity of PSMA-11 in the detection of metastatic lesions in patients with recurrent prostate cancer (18). Their results demonstrated a detection rate of 50% for patients with a PSA less than 1 ng/ml, and detection rate above 85% for patients with a PSA greater than 2 ng/ml. These detection rates are significantly higher than that reported by groups using choline (5).

Because of the improved resolution and image quality with PET, ability to quantitate uptake, increased sensitivity compared to choline, we intend to evaluate the utility of Ga-68 PSMA-11 for the imaging of prostate cancer. We expect that the data from this study will support applications for clinical approval of this imaging agent, leading to wider availability within the United States.

1.3 Previous experience with PSMA-11

We have completed numerous trials evaluating ⁶⁸Ga-PSMA-11 at UCSF and in conjunction with other institutions. These studies are currently being developed into an NDA application for submission to the FDA.

2 Objectives of the Study

2.1 Primary

- Sensitivity on a per-patient and per-region-basis (Table 1) of ⁶⁸Ga-PSMA-11 PET for detection of tumor location confirmed by histopathology/biopsy, clinical and conventional imaging follow-up.

3 Study Design

3.1 Characteristics

This is a prospective, single center, open-label study in patients with prostate cancer. Eligible participants will undergo baseline assessments at enrollment. Study participants will receive a one-time administration of Ga-68 PSMA-11 and undergo a PET/CT or PET/MRI imaging study.

3.2 Number of Subjects

It is anticipated that 1,000 patients will be enrolled in this study.

3.3 Eligibility Criteria

Patients must have baseline evaluations performed prior to the administration of the radiopharmaceutical and must meet all inclusion and exclusion criteria. In addition, the patient must be thoroughly informed about all aspects of the study, including the study visit schedule and required evaluations and all regulatory requirements for informed consent. The written informed consent must be obtained from the patient prior to enrollment. The following criteria apply to all patients enrolled onto the study:

3.3.1 Inclusion Criteria

1. Male, age \geq 18.
2. Histopathologically proven prostate adenocarcinoma.
3. Concern for metastatic disease in one of the following settings:
 - a. Initial staging with intermediate to high risk prostate cancer.
 - b. Biochemical recurrence after initial therapy.
4. Ability to understand a written informed consent document, and the willingness to sign it.

3.3.2 Exclusion Criteria

1. Patient unlikely to comply with study procedures, restrictions and requirements and judged by the Investigator to be unsuitable for study participation.

3.4 Duration of Follow Up

There will be no follow-up as part of this protocol.

3.5 Study Timeline

3.5.1 Primary Completion

The study will reach primary completion 24 months from the time the study opens to accrual.

3.5.2 Study Completion

The study will reach study completion 24 months from the time the study opens to accrual.

4 Study Drugs

4.1 Description, Supply and Storage of Investigational Drugs

4.1.1 Investigational Drug #1

Ga-68 labeled PSMA-11 (or PSMA-HBED-CC) is a radiopharmaceutical that will be produced under cGMP.

5 Treatment Plan

5.1 Dosage and Administration

The imaging agent (Ga-68 PSMA-11 or PSMA-HBED-CC) will be administered on an outpatient basis. It will be administered a single time intravenously prior to the PET imaging. The injected dose will be 3 to 7 mCi \pm 10% of ^{68}Ga -PSMA-11.

5.1.1 Other Modality(ies) or Procedures

5.1.1.1 PET imaging

a) ^{68}Ga -PSMA-11 PET preparation and injection:

The intravenously injected dose will be 111-259 MBq (3-7 mCi \pm 10%) of ^{68}Ga -PSMA-11 PET. A dose of 20 mg of furosemide (Lasix) is recommended to be injected i.v. together with, shortly before or after administration of the radiotracer in order to minimize PET scatter artifacts from excreted radiotracer accumulation in the kidney and urinary bladder that can occur with the gallium-68 radionuclide. Oral hydration is recommended on the day of the scan. Voiding is recommended immediately before start of the scan. Furosemide should not be administered in patients with medical contraindications to Furosemide administration including allergies and adverse reactions including sulfa allergies. (Note: Application of Furosemide can be omitted as part of the PET imaging protocol if a second-generation scatter correction algorithm is available for the PET scanner used in this protocol). PET imaging will begin 50-100 minutes after injection, but may be possible in certain circumstances for imaging to be delayed due to patient workflow or equipment issues. Scan time per bed position will be determined based on each sites PET scanner capabilities.

b) Patient preparation: no fasting is required.

c) PET protocol: Scan coverage will extend from mid thigh to the base of the skull, starting from the mid-thighs to prevent urinary bladder radiotracer accumulation at the start of PET imaging. Bed position scan time will be dependent on each sites scanner capabilities. At a minimum, 3 minutes per bed position will be used. In certain

circumstances, coverage may be extended to the toes. Contrast may be administered if requested by the referring clinician and is decided site dependent.

5.2 Monitoring and Toxicity Management

Each patient receiving Ga-68 PSMA-11 will be evaluable for safety. The safety parameters include spontaneous reports of adverse events reported to the investigator by patients.

6 Study Procedures and Observations

6.1 Schedule of Procedures and Observations

Screening assessments must be performed within 90 days prior to the first dose of investigational product. Any results falling outside of the reference ranges may be repeated at the discretion of the investigator. Treatment or visit delays for public holidays or weather conditions do not constitute a protocol violation.

A written, signed, informed consent form (ICF) and a Health Insurance Portability and Accountability Act (HIPAA) authorization must be obtained before any study-specific assessments are initiated. A copy of the signed ICF will be given to the subject and a copy will be filed in the medical record. The original will be kept on file with the study records.

Data collected from the study visits will be stored in a study-specific Research Electronic Data Capture (REDCap) system.

6.1.1 Screening Assessments

The screening procedures and assessments must be completed within 90 days of the Day 1 Visit.

1. PSA.
 - A clinically drawn PSA that was performed prior to the patient signing the ICF, but was performed within the screening window, may be used as the Screening PSA.

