6.2 Prohibited Medications

There are no prohibited medications.

7 Reporting and Documentation of Results

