8.1 Study Endpoints

Detection rate stratified by PSA level.

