8.3 Analyses Plans

8.3.1 Analysis of Primary Endpoints

Based on local reads for the detection of metastatic disease, the rate of localization abnormal focus of radiotracer will be stratified based upon the PSA prior to imaging.

9 Study Management

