Appendix 1 Schedule of Study Procedures and Assessments

	Screening (Day -90 to Day 1)	Imaging (Day 1)
Informed Consent	X	
Inclusion/Exclusion Criteria Assessment	X	
PSA	X	
⁶⁸ Ga-PSMA-11 Administration		X
Imaging (PET/CT or PET/MRI)		X
Adverse Event Collection		X

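### Does a stratifying PSA up to 90 days old bias the low-PSA detection rates enough to need a change?

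*Combined protocol and SAP*

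**What the plan says.** Section 8.1 gives the endpoint as "Detection rate stratified by PSA level". Section 8.3.1 is the whole analysis rule: using local reads, "the rate of localization abnormal focus of radiotracer will be stratified based upon the PSA prior to imaging". It gives no PSA cut points and no rule for choosing between two qualifying values.

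The only scheduled PSA is the screening one. Section 6.1 says "Screening assessments must be performed within 90 days prior to the first dose of investigational product", and Section 6.1.1 repeats the limit: "The screening procedures and assessments must be completed within 90 days of the Day 1 Visit". A routine clinical PSA drawn before consent is accepted if it falls inside that window. The Appendix 1 schedule marks PSA at screening and not on the imaging day.

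Two further provisions bear on the point. Section 6.1 adds "Any results falling outside of the reference ranges may be repeated at the discretion of the investigator", without a reference range for PSA. Section 6.2 says "There are no prohibited medications". No section describes recording therapy started between the PSA and the scan.

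**The concern.** The variable that defines the strata may be three months out of date at the scan. Section 3.3.1 admits men with biochemical recurrence, in whom PSA is usually rising, so an old value tends to understate the value at imaging. A patient recorded at 0.8 ng/ml might be above 1 ng/ml when scanned, and his greater chance of a positive scan would be credited to the lowest stratum.

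That stratum matters to the protocol's argument. Section 1.2 cites 50% detection below 1 ng/ml and above 85% over 2 ng/ml from an earlier study, and sets these against lower rates with choline. Sections 1.1 and 1.2 expect the data to support approval and to be pooled with other institutions' data. A bias from stale values would not shrink with enrolment. The free choice among repeats and the absence of any medication restriction appear to loosen the link between PSA and scan further.

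**Working it through.** **The plan's own figure.** Section 8.2 gives 500 patients a year for two years: 500 × 2 = 1,000. This is accrual arithmetic with no precision target or stratum sizes, so it does not settle the question.

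**Inputs from the protocol.** Maximum PSA age of 90 days (Sections 6.1 and 6.1.1). Background detection of 50% below 1 ng/ml and above 85% over 2 ng/ml (Section 1.2; 85% used here).

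**Assumptions, none of them in the documents.** Strata below 1, 1 to 2 and above 2 ng/ml. PSA at imaging lognormal with median 2 ng/ml and log-SD 1.2. Doubling time (DT) of 3, 6 or 12 months. PSA age either 90 days for everyone or uniform over 0 to 90 days. Detection follows either a step model (50%, 67.5%, 85% by stratum) or a logistic curve in log PSA through 50% at 0.5 ng/ml and 85% at 2 ng/ml.

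**Drift.** Growth over t days = 2^(t / 30.4375 / DT). For t = 90 and DT = 3 this is 2^0.986 = 1.98, so any recorded value above 1/1.98 = 0.51 ng/ml would be at or above 1 ng/ml at the scan.

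**Effect on the lowest stratum.** In the step model the patients wrongly recorded below 1 ng/ml are truly between 1 and 2 ng/ml. The apparent rate is therefore 50% + share misfiled × (67.5 − 50) points. For DT = 3 with every PSA 90 days old: 50 + 0.433 × 17.5 = 57.6%. Each pair below gives all PSAs 90 days old first, then uniform ages.

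| DT (months) | Growth in 90 days | Recorded <1 but truly ≥1 | Apparent <1 rate, step model (true 50%) | Rise, logistic model (true 49.3%) |
|---|---|---|---|---|
| 3 | 1.98 | 43% / 27% | 57.6% / 54.7% | +12.6 / +7.3 points |
| 6 | 1.41 | 27% / 15% | 54.7% / 52.7% | +6.8 / +3.6 points |
| 12 | 1.19 | 15% / 8% | 52.6% / 51.4% | +3.5 / +1.9 points |

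The middle stratum moves too: at DT = 6 with uniform ages, 67.5% becomes 71.9%. The most extreme case examined (logistic model, median PSA 5 ng/ml with log-SD 1.3, DT = 3, every PSA 90 days old) goes from 52.5% to 66.9%.

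**Scale.** The 95% half-width at a 50% rate is 1.96 × √(0.25/250) = 6.2 points with 250 patients in a stratum, and 4.4 points with 500.

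**Treatment in the gap.** Suppose therapy halves PSA in every patient between draw and scan. The recorded value is then twice the true one, so nobody recorded below 1 ng/ml is truly above it, and 18% of those recorded at or above 1 ng/ml are truly below. The apparent rate below 1 ng/ml is 50.0% in the step model (no bias) and 33.9% in the logistic model (true 49.3%). If 30% of patients are treated this way and the rest have DT = 6 with uniform ages, the rise falls from +2.7 to +2.3 points (step) or from +3.6 to +1.1 points (logistic).

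**What the obvious remedy would do.** Naming the last PSA before injection changes nothing for a patient with a single value 80 days old. Restricting to PSAs within 30 days does reduce the bias: with median PSA 2 ng/ml, the step model and uniform ages, the apparent rates become 51.8%, 51.0% and 50.5% for DT 3, 6 and 12, against 54.7%, 52.7% and 51.4%. But that describes a subset chosen by the analyst and leaves the primary estimate as it was.

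**The case for a change.** The best case for a change is that it costs little. One sentence in Section 8.3.1, the PSA date, a note of intervening systemic therapy and a sensitivity analysis by PSA-to-scan interval would need no extra blood draw and no change to eligibility. For untreated rising PSA the direction of bias is clear, and at short doubling times its size is comparable with sampling error. If therapy started in the gap is not recorded, its effect cannot be examined later.

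Much of this stands. The 90-day window is real, the selection rule is unwritten, and an untreated rise would flatter the low strata. Three parts do not carry through.

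- The error is not one-directional. Therapy started in the gap pushes the other way. A repeat is drawn later, so using it shortens the lag. A free choice between two values has no fixed direction.
- The size cannot be taken from the protocol. Cut points, PSA distribution, doubling times and actual PSA ages are all assumed. The rising-PSA model suits recurrence best, while Section 3.3.1 also admits initial staging and gives no split.
- The stated target is detection by the PSA available before imaging. That is a coherent quantity, and it is the value a referring clinician has in hand. Calling a value misclassified presupposes a different target, PSA at the moment of injection.

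**Conclusion.** No change is needed. Where several values qualify, "will be stratified based upon the PSA prior to imaging" is most naturally read as the latest one before the scan, and analysts would fill the gap that way. Compliance with the 90-day limit cannot be checked without the date of the PSA, so the lag should be recoverable for a descriptive breakdown if anyone wants one. Accepting a routine clinical PSA is a fair trade-off in a 1,000-patient, single-visit imaging study.

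With median PSA 2 ng/ml, cuts at 1 and 2 ng/ml, ages uniform over the window and no treatment in the gap, the rise below 1 ng/ml is +1.4 to +7.3 points. It is larger if every PSA sits at the 90-day limit and smaller with slow kinetics, recent draws or intervening therapy. The plan sets no hypothesis test, success threshold or choline comparison that such a shift could overturn. The available remedy would mostly write down the natural reading and add a subset analysis, leaving the primary estimate largely unchanged. When reporting, the age of the PSA is worth stating as a limitation.

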6.1.2 Treatment Period

6.1.2.1 Study Procedures, Imaging Day 1

- ⁶⁸Ga-PSMA-11 administration
- PET imaging using either PET/CT or PET/MRI
- Administration of intravenous contrast (for MRI or CT as clinically indicated)
- Evaluation of adverse events

6.2 Prohibited Medications

There are no prohibited medications.

7 Reporting and Documentation of Results

7.1 Evaluation of Side Effects

7.1.1.1 Definitions

Evaluable for toxicity

All patients will be evaluable for toxicity from the time of ⁶⁸Ga-PSMA-11.

7.2 Evaluation of Safety

Analyses will be performed for all patients receiving ⁶⁸Ga-PSMA-11. The study will use the [CTCAE v4.0](#) for reporting of adverse events.

7.3 Definitions of Adverse Events

7.3.1 Adverse Event

An adverse event (also known as an adverse experience) is defined as any untoward medical occurrence associated with the use of a drug in humans, whether or not considered drug related. More specifically, an adverse event (can be any unfavorable and unintended sign (e.g., an abnormal laboratory finding), symptom, or disease temporally associated with the use of a drug, without any judgment about causality. An adverse event can arise from any use of the drug (e.g., off-label use, use in combination with another drug) and from any route of administration, formulation, or dose, including an overdose.

7.3.2 Adverse Reaction

An adverse reaction is defined as any adverse event caused by the use of a drug. Adverse reactions are a subset of all suspected adverse reactions for which there is reason to conclude that the drug caused the event.

